Subject Participation Duration	6 months
Single or Multi-Site	Single site
Objectives	To evaluate the safety of acamprosate in individuals with alcohol-use disorder (AUD) and alcohol-related liver disease
Number of Subjects	10
Diagnosis and Main Inclusion Criteria	Adult patients aged 21 or over with a diagnosis of alcohol-related liver disease and AUD
Study Product, Dose, Route, Regimen	Acamprosate will be dosed at 333 mg TID, increased to 666 mg TID after 1 week if tolerated. If GFR is 30-50 ml/min, dosage will remain at 333 mg TID throughout the study.
Duration of Administration	3 months
Reference therapy	No reference or control group
Statistical Methodology	Basic descriptive statistics and a qualitative analysis will be performed

1 Introduction

This document is a clinical research protocol for a human research study. This study will be carried out in accordance with the applicable United States government regulations and Mayo Clinic research policies and procedures.

1.1 Background

Alcohol use disorder (AUD) is a common condition with a lifetime and 12-month prevalence of 29.1% and 13.9%, respectively, identified in the US population (Grant et al., 2015). Although several effective treatments are available, less than one-fifth of individuals seek treatment over their lifetime; most seek help from physicians to manage comorbidities related to AUD (Grant et al., 2015; Lyon, 2017). Alcohol-related liver disease encompasses a wide spectrum of disease, ranging from steatosis and minimal fibrosis to alcoholic hepatitis, cirrhosis and sequelae of portal hypertension. Hepatic steatosis is common, seen in approximately 90% of longstanding heavy drinkers with recent binging (Edmondson et al., 1967). Ongoing alcohol consumption may result in steatohepatitis in one third of patients and an estimated 16% of those with steatohepatitis will develop cirrhosis over five years (Barrio et al., 2004; Deleuran et al., 2012). Individuals with alcohol-related cirrhosis are at high risk for complications from liver disease and death; these risks are increased in the setting of ongoing alcohol use (Jepsen et al., 2010; Jepsen et al., 2012).

Despite the prevalence of liver disease complicating AUD, there are few prospective clinical studies evaluating the efficacy of pharmacologic treatments to promote abstinence and prevent relapse. Naltrexone and acamprosate have been found to be effective for AUD; however, naltrexone carries a significant risk of hepatocellular injury, and it is contraindicated in those with acute hepatitis or liver failure (Jonas et al., 2014; Alkermes, Inc., 2010). Other promising medications that require further study include baclofen, topiramate, gabapentin, varenicline and ondansetron, of which baclofen is the only drug that has been evaluated in liver disease (Addolorato et al., 2007).

Acamprosate has not been evaluated formally in individuals with AUD and liver disease. It is an N-methyl-D-aspartate glutamate receptor antagonist approved by the Food and Drug Administration to aid in maintaining abstinence in individuals with alcohol dependence (Frye et al., 2016). Acamprosate has an unclear mechanism of action, although it is thought that its effect on decreased alcohol craving intensity is mediated through a reduction in glutamate levels (Frye et al., 2016). The efficacy of acamprosate has been demonstrated in several meta-analyses, most recently exhibiting a number needed to treat of 12 to prevent return to any drinking (Jonas et al., 2014; Rosato et al., 2015). Acamprosate is not metabolized by the liver and thus has been considered as a potential therapeutic option in those with liver disease. However, as acamprosate antagonizes the glutamate receptor, there have been concerns it may increase the risk of hepatic encephalopathy. Previously, a single dose of acamprosate 666 mg was administered to 12 patients with Child-Pugh A or B cirrhosis with no identifiable induction of subclinical hepatic encephalopathy; however, transient diastolic hypotension was noted (Delgrange et al., 1992). No further studies on acamprosate have been performed in individuals with liver disease.

To evaluate the safety of acamprosate in individuals with AUD and alcohol-related liver disease, an initial pilot study in five patients with a Model for End Stage Liver Disease Sodium (MELD-Na) score less than 20 will be conducted. If no safety concerns are identified, the study will then

be performed in five patients with MELD-Na scores of 20 or more. If again no safety concerns are identified, a larger, placebo-controlled efficacy study is planned and will be submitted as a separate protocol.

1.2 Investigational Agent

Per the manufacturer, Merck (2005): “*CAMPRAL*® (acamprosate calcium) is supplied in an enteric-coated tablet for oral administration. Acamprosate calcium is a synthetic compound with a chemical structure similar to that of the endogenous amino acid homotaurine, which is a structural analogue of the amino acid neurotransmitter γ -aminobutyric acid and the amino acid neuromodulator taurine. Its chemical name is calcium acetylaminopropane sulfonate. Its chemical formula is C10H20N2O8S2Ca and molecular weight is 400.48.

Each *CAMPRAL* tablet contains acamprosate calcium 333 mg, equivalent to 300 mg of acamprosate. Inactive ingredients in *CAMPRAL* tablets include: crospovidone, microcrystalline cellulose, magnesium silicate, sodium starch glycolate, colloidal anhydrous silica, magnesium stearate, talc, propylene glycol and Eudragit® L 30 D or equivalent. The drug product will appear in tablet form.”

Acamprosate is now available as a generic in the USA.

1.3 Preclinical Data

n/a

1.4 Clinical Data to Date

Acamprosate has been studied extensively in individuals without liver disease. The efficacy of acamprosate has been demonstrated in several meta-analyses, most recently exhibiting a number needed to treat of 12 to prevent return to any drinking (Jonas et al., 2014; Rosato et al., 2015).

Previously, a single dose of acamprosate 666 mg was administered to 12 patients with Child-Pugh A or B cirrhosis with no identifiable induction of subclinical hepatic encephalopathy; however, transient diastolic hypotension was noted (Delgrange et al., 1992). No further studies on acamprosate have been performed in individuals with liver disease.

1.5 Dose Rationale

Acamprosate will be dosed at 333 mg TID, increased to 666 mg TID after 1 week if tolerated. If GFR is 30-50 ml/min, dosage will remain at 333 mg TID throughout the study. The dosing and dose regimen of acamprosate has varied in prior trials; however, the regimen used herein is largely considered standard for use in AUD (Plosker, 2015; Higuchi, 2015). Based on prior studies and for practical purposes, route of administration will be by mouth.

1.6 Risks and Benefits

Individuals with alcohol-related cirrhosis are at high risk for complications from liver disease and death; these risks are increased in the setting of ongoing alcohol use (Jepsen et al., 2010; Jepsen et al., 2012). A profound difference in five-year survival after an episode of alcoholic hepatitis is seen in those who are able to maintain abstinence compared to those who continue to drink or relapse, with rates of 75% and 21-27%, respectively (Potts et al., 2013).

Adverse events associated with acamprosate use are considered minimal and primarily have included anxiety, diarrhea and vomiting (Jonas et al., 2014; Reus et al., 2018). Specific rates of the following adverse events have been reported: pruritus (4%), diarrhea (17%), flatulence (3%), nausea (4%), dizziness (3%), insomnia (7%), anxiety (6%) and depression (5%) (Merck, 2005). More rare risks include cardiomyopathy, deep thrombophlebitis, heart failure, mesenteric arterial occlusion, shock and suicide (Merck, 2005). There has been no increased risk of withdrawal from trials with acamprosate due to adverse events (Jonas et al., 2014). Given the high risk of adverse outcomes associated with ongoing alcohol consumption in this patient population, including death, the risks of acamprosate use are reasonable in comparison.

2 Study Objectives

Primary Objective:

To assess the safety and tolerability of acamprosate for treatment of AUD in alcohol-related liver disease as measured by adverse event reporting.

Secondary Objective:

To assess treatment effect of acamprosate on alcohol relapse in alcohol-related liver disease as measured by Pennsylvania Alcohol Craving Scale (PACS) scores and reporting of alcohol use.

3 Study Design

This study is a phase IIa trial of the safety of acamprosate in treating AUD in alcohol-related liver disease. Subjects will be screened for eligibility at outpatient clinic visits and during hospitalizations; interested qualified subjects will be consented and offered participation in this trial. At study enrollment, initial MELD-Na score must be less than 20 for the five individuals enrolling in the first phase of the pilot safety assessment. The second phase of the pilot safety assessment will include individuals with a MELD-Na of 20 or more at enrollment. Once consent has been obtained, baseline characteristics will be established and then patients will be initiated on acamprosate treatment. Acamprosate will be administered for three months, during which time, patients will complete monthly blood work, weekly telephone assessments for the first month, followed by telephone assessments and urine testing on a monthly basis thereafter. A final clinic visit for evaluation and collection of lab samples will be conducted at the end of the study at 3 months. Patients will be contacted by telephone at weeks 13 and 24 after study enrollment for final follow up assessments off of study medication.

3.1 General Description

Adult patients aged 21 or over with a diagnosis of alcohol-related liver disease and AUD will be identified in the outpatient clinic or while admitted to hospital and seen by the gastroenterology or hepatobiliary service at Mayo Clinic, Rochester. This population is evaluated for potential eligibility for other alcohol-related liver disease studies by a research coordinator on a weekly basis. The diagnosis of alcohol-related liver disease will be determined by a hepatologist based on history of regular and excessive alcohol consumption in the absence of other causes of liver cirrhosis or acute hepatitis, compatible clinical, imaging and laboratory findings and typical histology on liver biopsy, if performed. Underlying liver disease may include alcoholic hepatitis, advanced (F3-F4) fibrosis, and/or portal hypertension. The diagnosis of AUD will be determined by a hepatologist based on history obtained that is consistent with DSM-5 diagnostic criteria for AUD (all categories of mild, moderate and severe considered eligible).

Patients need not be abstinent from alcohol prior to initiating acamprosate treatment (but not abstinent for more than 6 months). At study enrollment, initial MELD-Na score must be less than 20 for the five individuals enrolling in the first phase of the pilot safety assessment. The second phase of the pilot safety assessment will include individuals with a MELD-Na of 20 or more at enrollment. Patients with heart failure (NYHA class II or higher) or hypotension requiring the use of vasoconstrictors (i.e. midodrine) will be excluded. Individuals with a glomerular filtration rate (GFR) of less than 30 ml/min will be excluded. Acamprosate will be dosed at 333 mg TID, increased to 666 mg TID after 1 week if tolerated. If GFR is 30-50 ml/min, dosage will remain at 333 mg TID throughout the study. Acamprosate will be administered for a total of 3 months.

Prior to enrollment, known risks and benefits of acamprosate in treating AUD will be discussed with patients including pruritus (4%), diarrhea (10% to 17%), flatulence (3%), nausea (4%), dizziness (3%), insomnia (7%), anxiety (6%) and depression (5%). More rare risks include cardiomyopathy, deep thrombophlebitis, heart failure, mesenteric arterial occlusion, shock and suicidal intent (1%).

At enrollment, collected baseline characteristics will include patient age, sex, race, marital and employment status, education level, social support, presence of children, age of children, underlying liver disease etiology, MELD-Na score, presence of ascites, esophageal varices, spontaneous bacterial peritonitis, diabetes, corticosteroid or other medical treatment for alcoholic hepatitis (Maddrey and Lille scores if relevant), medical comorbidities, prescription and non-prescription medications. With regard to alcohol use, patients will have the 11 DSM-5 questions regarding AUD answered at screening (American Psychiatric Association, 2013), as well as the following history obtained: duration of excess alcohol consumption in years, level of alcohol consumption prior to study enrollment, interval of alcohol abstinence prior to study enrollment, family history of alcoholism, history of alcohol-related legal issues, psychiatric comorbidity (requiring medication, outpatient care or hospitalization), other addictions including smoking and number of prior rehabilitation attempts for alcohol or other addictions. The PACS questionnaire will be administered. Vital signs and a physical examination will be performed. West Haven HE score will be graded and modified telephone version of MMSE completed. Blood work will be completed including a complete blood count, electrolytes, creatinine, blood urea nitrogen, total bilirubin, direct bilirubin, albumin, INR, AST, ALT and alkaline phosphatase. A urine ethyl

glucuronide will be performed. A urine pregnancy test will be conducted before admission into the trial for women of child-bearing potential.

Study duration will be six months. During the study, patients will complete monthly MELD-Na labs and receive a phone call weekly for the first month, then monthly for a total of 3 months. Urine ethyl glucuronide will be done at enrollment and once monthly. Patients will then have a follow up visit at 12 weeks, with labs, urine ethyl glucuronide, vital signs and physical exam. During telephone assessments and at the follow up visit, patients will be asked about potential side effects and hepatic decompensation. Other variables to be collected at enrollment and at the 3 month visit include Child-Pugh score, West Haven grading of HE, vital signs at enrollment and current medications. At enrollment, during phone calls and at the follow up visit, patients will be asked standardized questions to assess for HE based on the abbreviated telephone version of the mini-mental state examination (MMSE). Follow up telephone visits at 13 and 24 weeks will be conducted, primarily to monitor for adverse events and alcohol relapse.

The Pennsylvania Alcohol Craving Scale (PACS) will be applied before treatment initiation, weekly for the first month on treatment, then monthly thereafter. This will include the need severity scale (mild, moderate, severe) at baseline and at each assessment by phone call and in clinic.

Alcohol use relapse will be monitored. Any amount of alcohol use as revealed during follow-up considered a relapse event. Alcohol use will be captured and categorized as none, slip (no longer drinking at most recent follow up) or sustained alcohol use (minimum 100 days drinking). Slips and sustained alcohol use will be categorized as binge drinking, frequent drinking, or both (binge drinking as more than 6 units/day for men and 4 units/day for women and frequent drinking as alcohol use in 4 or more days/week regardless of quantity per day) (Lee et al., 2018).

Basic descriptive statistics and a qualitative analysis will be performed. Analyses will be performed using SPSS 25 (Chicago, IL). Results will not contain any patient-specific information.

3.2 Number of Subjects

10 individuals.

3.3 Duration of Participation

6 months.

3.4 Primary Study Endpoints

The primary endpoint is an estimation of the safety profile of acamprosate for treatment of AUD in alcohol-related liver disease as measured by adverse event reporting. The safety parameters to be measured include clinical symptoms, vital signs, physical examination, blood work and urine testing.

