7.2 Statistical Methods

Descriptive Statistics

Univariate descriptive statistics and frequency distributions will be calculated, as appropriate for all variables. Baseline values for demographic, clinical, and outcome variables (primary and secondary) will be tabulated.

Safety analyses will be conducted using all subjects, and presented overall. Safety data will be analyzed using descriptive statistics and tabulation.

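### The primary endpoint is called an estimation of safety, but no proportion is named, no interval is planned, and the two MELD-Na cohorts are reported only together

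*Combined protocol and SAP*

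**What the plan says.** **Endpoint.** Section 3.4 states: "The primary endpoint is an estimation of the safety profile of acamprosate", measured through adverse event reporting. It adds: "The safety parameters to be measured include clinical symptoms, vital signs, physical examination, blood work and urine testing". These five domains are not ranked, and no event, proportion or other summary is singled out. Section 3.6 only refers back to 3.4.

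**Analysis.** Section 7.2 states: "Safety data will be analyzed using descriptive statistics and tabulation". The safety results are to be shown overall, with no split by cohort. Section 7.1 reports that no power analysis was done. Section 7.3 analyses everyone who took at least one dose.

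**Size.** Section 3.2 gives "10 individuals". Section 4.4.1 replaces withdrawn patients until ten complete, so more than ten may be dosed.

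**Use of the result.** Section 1.1 describes "an initial pilot study in five patients" with MELD-Na below 20. It continues "If no safety concerns are identified, the study will then" move to five patients with MELD-Na of 20 or more. The next step follows: "If again no safety concerns are identified, a larger, placebo-controlled efficacy study is planned". Neither step defines a safety concern.

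**The concern.** An estimation endpoint needs a named quantity and a statement of how precisely it is known. This plan gives neither, so readers of the final report would have to choose their own headline from many tabulated items.

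Precision matters here because the result informs two decisions and the groups are very small. A count of zero in five or ten patients is compatible with a wide range of true risks, and a bare table does not show that range. Pooled presentation adds a second problem. The cohorts were separated on purpose by disease severity, yet the report would not show how little is known about the sicker five on their own.

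**Working it through.** **Inputs.** Cohort sizes 5 and 5, total 10 (sections 1.1 and 3.2). The denominator is all patients dosed (7.3), possibly above 10 because of replacement (4.4.1). The documents give no confidence level, so two-sided 95% is my assumption; one-sided 95% is shown as a variant.

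**The plan's own figure.** Ten patients is stated without an event rate, precision target or power, so there is no derivation to reproduce.

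**Upper limit when no event of a given type is seen.** The exact (Clopper-Pearson) limit solves (1 − p)^n = 0.025, so p = 1 − 0.025^(1/n). For the one-sided variant, 0.05 replaces 0.025.

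| Patients | Two-sided 95% | One-sided 95% |
|---|---|---|
| 5 (either cohort alone) | 1 − 0.025^(1/5) = 52.2% | 45.1% |
| 10 (both cohorts pooled) | 1 − 0.025^(1/10) = 30.8% | 25.9% |
| 12 (ten plus two replacements, as an illustration) | 1 − 0.025^(1/12) = 26.5% | 22.1% |

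The pooled rows assume one common rate across the two MELD-Na groups. Without that assumption, the limit for the sicker cohort stays at 52.2% when its five patients show no event.

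**Chance of seeing no event at a given true risk**, (1 − p)^n:

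- True risk 20%: 0.8^5 = 32.8% in five patients, 0.8^10 = 10.7% in ten.
- True risk 10%: 0.9^5 = 59.0% in five patients, 0.9^10 = 34.9% in ten.

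**When the count is not zero.** One event gives an exact 95% interval of 0.5% to 71.6% for 1/5, and 0.3% to 44.5% for 1/10. This case matters because under 8.5 a single attributable grade 3 event that is not serious does not reach the study-level count of two patients.

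**Reading counts against the listed rates.** Four of ten patients with diarrhea would give 40%, with an exact interval of 12% to 74%. That contains the 17% listed in section 1.6, but not the lower end of the 10% to 17% listed in section 3.1. The comparison depends on which listed figure is used, and a table without an interval shows neither reading.

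**The case against.** The study is openly a descriptive pilot, and nothing in it claims power. Exact intervals can be worked out by anyone from n/N, and leaving them out biases no result. That stands, and it is why the point concerns the undefined quantity and the missing precision, not the sample size. An exact interval is itself a descriptive statistic.

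A reader might infer that the plan treats zero events in five or ten patients as proof that the drug is safe. The documents do not support this. Section 1.1 speaks of concerns being identified, does not equate that with zero events, and leads to a further controlled study under a separate protocol.

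Nor does progression rest on a table alone. Section 8.5 puts the study on hold for DSMB review after one serious adverse event. It stops the study for a serious event rated at least possibly related, for two patients with attributable grade 3 or higher events, for three with AST or ALT above 500 U/L, or on DSMB recommendation. The DSMB charter cited in 8.6.1 is not in the text and may define the cohort review. These safeguards are real, but the protocol does not tie them to the two steps in 1.1, and they supply no estimate.

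Another tempting remedy is to replace the condition in 1.1 with an upper limit. That would not work: the documents give no threshold, and with five patients the best attainable two-sided limit is 52%.

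Finally, a headline proportion is not ready-made in the plan. Section 8.2 uses CTCAE version 5.0, while 8.3.1 mentions a 1–5 severity scale and then defines three levels. Relatedness is rated by the principal investigator in 8.3.1, but by the investigator or the study adjudicator in different rules of 8.5. Section 8.1 leaves some hospitalizations for the target disease out of adverse event reporting. These points must be settled in the definition.

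**Conclusion.** The concern holds as a gap in estimation and reporting. The primary endpoint has no named proportion, no interval and no presentation by cohort, although its result informs two progression steps.

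In the zero-event case, true rates up to 52% remain open for either cohort of five, and up to 31% for ten pooled (26.5% for twelve). These figures rest on an assumed two-sided 95% level, on independent patients and, for the pooled figures, on a common rate across the MELD-Na groups. They say nothing about outcomes with one or more events, and they do not show that the safeguards in 8.5 are inadequate. The trial can run as designed. What changes is what can be concluded from it.

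**What to change.** 1. **Sections 3.4 and 7.2:** name one headline proportion: patients with at least one serious adverse event or CTCAE grade 3 or above event that is rated at least possibly related, out of all patients dosed. State that CTCAE version 5.0 grading applies, whose relatedness rating counts, and how the hospitalizations that 8.1 leaves out are handled.
2. **Section 7.2:** report this proportion, hepatic encephalopathy (the specific worry raised in 1.1, with its event definition stated) and each listed adverse event as n/N with an exact (Clopper-Pearson) 95% interval, for each MELD-Na cohort and overall.
3. **Section 1.1:** keep the progression condition and reconcile it with the rules in 8.5, so that the reader can tell how the two relate. Require any statement that no safety concerns were found to carry the upper limit still compatible with the data.

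The cost is a few lines of text and minutes of programming, with no change to sample size, visits or treatment. The downside is a less favourable-looking conclusion, since the intervals by cohort will be wide.
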